NGS	Next Generation Sequencing	
NTL	Non-Target Lesion	
OAE	Other Significant Adverse Event (see definition in Section 8.3.6)	
ORR	Objective Response Rate	
OS	Overall Survival	
PARP	Poly-adenosine 5'diphosphoribose (ADP) Polymerase / Polymerisation	
PD	Progression of Disease	
PFI	Progression-Free Interval	
PFS	Progression Free Survival during initial olaparib maintenance therapy	
PFS2	Progression Free Survival following initial olaparib maintenance and subsequent chemotherapy	
PI	Principal Investigator	
p.o.	Administered by mouth	
PR	Partial Response	
PRO	Patient Reported Outcome	

Abbreviation or special term	Explanation
PSR	Platinum Sensitive Relapsed
QoL	Quality of Life
RECIST	Response Evaluation Criteria In Solid Tumours
SAE	Serious Adverse Event (see definition in Section 6.2)
SAP	Statistical Analysis Plan
s BRCA m	Somatic tumour BRCA mutated (mutation detected in the tumour but not in the germline)
sBRCAwt	Somatic tumour BRCA wild type
SD	Stable Disease
SGOT	Serum Glutamic Oxaloacetic Transaminase
SGPT	Serum Glutamic Pyruvate Transaminase
SSB	Single Strand Breaks
TDT	Time to Discontinuation of Treatment or Death
TFST	Time to First Subsequent Therapy (Treatment) or Death
TL	Target Lesion
TOI	Trial Outcome Index
TSST	Time to Second Subsequent Therapy (Treatment) or Death
ULN	Upper Limit of Normal
US	United States
WBDC	Web Based Data Capture
wt	Wild type.
	Patients without evidence of BRCA 1 or BRCA 2 deleterious or suspected deleterious mutations for a given gene or set of genes (e.g. BRCA 1 or BRCA 2)

1. **INTRODUCTION**

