All patients should have assessments until documented evidence of objective radiological progression according to RECIST 1.1 guidelines, irrespective of treatment decisions (i.e., radiological follow up until progression even if a patient discontinues olaparib prior to progression and/or receives a subsequent therapy prior to progression). CT examination with intravenous (i.v.) contrast media administration is the preferred imaging modality. MRI should only be used where CT is not feasible or it is medically contra-indicated. For brain lesion assessment, MRI is the preferred method. In addition, FDG-PET, bone scintigraphy and ultrasound may also be used for identifications of new lesions only.

At baseline, the imaging modalities used for assessment should be performed by contrast enhanced CT (MRI where CT is contraindicated) scans of the chest, abdomen and pelvis with other regions as clinically indicated for the assessment of disease. Follow-up CT or MRI

assessments will cover chest (in those patients with disease in the chest or upper abdomen lymphadenopathy at baseline), abdomen and pelvis with any other regions imaged at baseline where disease was present. Any other sites at which new disease is suspected should also be appropriately imaged.

Sites should use the same modality and acquisition parameters to assess a patient at baseline and at subsequent follow-up, in order to ensure longitudinal consistency.

Radiological examinations performed in the conduct of this study should be retained at site as source data.

There will be no central review of CT and MRI scans in this study. Radiological reading will be performed at the site level only. All treatment decisions will be based on site assessment of scans.

5.1.2 **Tumour Evaluation**

RECIST 1.1 guidelines are mandated to be used to assess patient response to treatment by determining progression free survival (PFS) times, objective response rates (ORR) and duration of response (DoR). The RECIST 1.1 guidelines for measurable, non-measurable, target and non-target lesions and the objective tumour response criteria (complete response, partial response, stable disease or progression of disease) are presented in Appendix F.

CA-125 should not be directly used for assessing objective response or progression and patients should be continued on treatment until objective radiological disease progression.

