8.2.2 Safety analysis set

The safety analysis set comprises all patients who received at least 1 dose of olaparib. All safety analyses will be based on the safety analysis set.

8.2.3 **PK analysis set**

Not applicable.

8.2.4 **PRO analysis set**

PRO analyses will be based on the FAS, with additional exclusion criteria, excluding:

- Patients who do not have any evaluable baseline data
- Patients who do not have any evaluable post-baseline data.

8.3 **Outcome measures for analyses**

8.3.1 **Calculation or derivation of efficacy variable(s)**

At each visit patients will be programmatically assigned a visit response of CR, PR, SD, PD, NE based on RECIST 1.1 guidelines or other methods depending on the status of their disease compared to baseline and previous assessments, based on the investigator assessment.

8.3.2 **Primary endpoint**

PFS is defined as the time from enrolment until the date of objective radiological disease progression (assessed via RECIST 1.1) or death (by any cause in the absence of disease progression) regardless of whether the patient withdraws from therapy or receives another anticancer therapy prior to disease progression. Patients who have not progressed or died at the time of analysis will be censored at the time of the latest date of assessment from their last

evaluable efficacy assessment. However, if the patient progresses or dies after two or more missed visits, the patient will be censored at the time of the latest evaluable assessment. Given the scheduled visit assessment scheme, two missing visits will equate to more than 26 weeks since the previous RECIST 1.1 assessment, allowing for early and late visits. If the patient has no evaluable visits or does not have a baseline assessment they will be censored at day 1 unless they die within two visits of baseline (25 weeks allowing for visit window).

The PFS time will always be derived based on scan/assessment dates not visit dates. Assessments/scans contributing towards a particular visit may be performed on different dates. The following rules will be applied:

- Date of progression will be determined based on the earliest of the assessment/scan dates of the component that triggered the progression.
- When censoring a patient for PFS the patient will be censored at the latest of the assessment/scan dates contributing to a particular overall visit assessment.

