8.3.3 Secondary endpoints

Overall Survival

Overall survival is defined as the time from the date of enrolment in the study until death due to any cause. Any patient not known to have died at the time of analysis will be censored based on the last recorded date on which the patient was known to be alive.

Note: Survival calls will be made in the week following the DCO for the analysis, and if patients are confirmed to be alive or if the death date is post the DCO date these patients will be censored at the date of DCO.

Time from enrolment to second progression (PFS2)

Time from enrolment to second progression is defined as the time from the date of enrolment to the earliest of the progression event subsequent to that used for the primary variable PFS or death. The date of second progression will be recorded by the investigator and defined according to local standard clinical practice and may involve any of objective radiological, symptomatic, CA-125 progression or death. Second progression status will be reviewed every 12 weeks following the progression event used for the primary variable PFS (the first progression) and status recorded. Patients alive and for whom a second disease progression has not been observed should be censored at the last time known to be alive and without a

second disease progression, i.e., censored at the last assessment for progression date if the patient has not had a second progression or death.

Time to first subsequent anti-cancer therapy or death (TFST)

As a supportive summary to PFS, time to start of first subsequent anti-cancer therapy or death will be assessed. Time to first subsequent therapy or death is defined as the time from the date of enrolment to the earlier of first subsequent therapy start date, or death date. Any patient not known to have had a further subsequent therapy or death will be censored at the last known time to have not received subsequent anti-cancer therapy.

Time to study treatment discontinuation or death (TDT)

Time to study treatment discontinuation or death (TDT) will be assessed. TDT is defined as the time from the date of enrolment to the earlier of the date of study treatment discontinuation or death. Any patient not known to have died at the time of analysis and not known to have discontinued study treatment will be censored based on the last recorded date on which the patient was known to be alive.

Time to second subsequent chemotherapy or death (TSST)

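### PFS2 is anchored to the progression used for PFS, which is not always the first progression: it comes out too long after a non-RECIST progression and has two readings after missed visits

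*Protocol*

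**What the plan says.** Section 8.3.3 runs PFS2 from enrolment to "the earliest of the progression event subsequent to that used for the primary variable PFS or death". The second progression is recorded by the investigator under local practice and "may involve any of objective radiological, symptomatic, CA-125 progression or death". The 12-weekly review for it starts "following the progression event used for the primary variable PFS (the first progression"; the bracketed gloss shows that the PFS event and the first progression were taken to be the same thing.

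The PFS event is narrower. Section 8.3.2 counts RECIST progression or death, "regardless of whether the patient withdraws from therapy or receives another anticancer therapy prior to disease progression". Section 5.1.1 keeps the scans going accordingly: "radiological follow up until progression even if a patient discontinues olaparib prior to progression and/or receives a subsequent therapy prior to progression". Section 8.3.2 also removes some progressions from PFS: "if the patient progresses or dies after two or more missed visits, the patient will be censored at the time of the latest evaluable assessment".

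Three other places bear on the meaning of PFS2:

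- The abbreviation list gives it as "Progression Free Survival following initial olaparib maintenance and subsequent chemotherapy".
- Section 4.3.3 takes the patient's status at first progression as the reference and does not mention the PFS event.
- Table 3 marks the second-progression row only in the column for patients beyond first progression, not in the column for patients off treatment who are still followed for it.

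**The concern.** The anchor admits one kind of progression (RECIST, not censored), while the endpoint admits several. Where a patient's first progression is of a kind that PFS does not count, the rule moves on to the wrong event.

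PFS2 is a named secondary endpoint in all *BRCA*m patients and in the s*BRCA*m cohort, and it is summarised at the PFS data cut-off. With one arm, a bias that lengthens it has no control arm to cancel against. The research hypothesis in section 1.2 is consistency with earlier controlled trials, so a lengthened median would flatter the comparison a reader will make. In a cohort of about 50 s*BRCA*m patients, 5 to 20% is 2.5 to 10 patients.

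**Working it through.** **The plan's own figures.** None is given for PFS2. Those for PFS reproduce: 0.60 × 250 = 150 and 0.60 × 50 = 30 events. The missed-visit limit, "two missing visits will equate to more than 26 weeks since the previous RECIST 1.1 assessment", is 2 × 12 + 1 + 1 = 26 weeks, from the 12-week schedule with 1-week windows. With exponential PFS (median 11.2 months) and 23 months of entry with cumulative accrual (t/23)^k, the 150th event falls at 27.6 months for uniform entry (k = 1) and at 31.0 to 32.6 months for back-loaded entry (k = 2 to 3). That agrees with about 32 months under non-linear recruitment. None of these figures uses the PFS2 rule.

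**Case 1: first progression not by RECIST.** Follow one patient through the rules:

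1. She has symptomatic or CA-125 progression on olaparib without RECIST progression and stops. Appendix F section 4.5 foresees stopping for symptomatic deterioration without objective progression. There is no PFS event.
2. She starts a first subsequent chemotherapy. This neither censors PFS nor counts as an event (8.3.2), and scans continue (5.1.1).
3. She progresses by RECIST on that chemotherapy. This is her second progression, but it is the one used for PFS.
4. She may start a second subsequent chemotherapy. That is her TSST event.
5. A third progression or death follows. Only now does 8.3.3 record PFS2.

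Under the abbreviation list, step 3 is PFS2. Under 8.3.3 it is step 5. TSST (step 4), which 8.3.3 calls a supportive summary to PFS2, can then come before PFS2.

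**Case 2: first RECIST progression after two or more missed visits.** Section 8.3.2 censors PFS at the last evaluable assessment, so no progression is used for PFS. Read literally, 8.3.3 then has no progression to count from. Read through its own gloss, or through 4.3.3, the recorded late progression serves as the first. Two analysts could derive different PFS2 times for the same patient. Death is an event under either reading.

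**Illustration of size for case 1.** Inputs:

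- First progression T1: exponential, median 11.2 months (section 8.1).
- Gap G2 to second progression: exponential, scaled so that the median of T1 + G2 is 23.8 months. That is the phase II median TSST on olaparib, which Appendix G calls an approximation of PFS2. It gives a G2 median of 8.56 months.
- Gap G3 from second to third progression: exponential, median 4, 6 or 9 months (assumed).
- Affected share q: 5, 10 or 20% (assumed).

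PFS2 is T1 + G2 for unaffected patients and T1 + G2 + G3 for the share q. Death before the later progression is ignored. Simulated medians (400,000 patients), against 23.8 months at q = 0:

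| G3 median (months) | q = 5% | q = 10% | q = 20% |
|---|---|---|---|
| 4 | 24.11 (+0.31) | 24.40 (+0.60) | 25.02 (+1.22) |
| 6 | 24.23 (+0.43) | 24.69 (+0.89) | 25.58 (+1.78) |
| 9 | 24.38 (+0.58) | 24.96 (+1.16) | 26.21 (+2.41) |

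**The case against.** **Few patients may be affected.** Section 5.1.2 says CA-125 should not be used directly to assess progression and asks for treatment until radiological progression. This stands as a limit on the number. It does not empty the group, because stopping for symptomatic deterioration is foreseen.

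**The abbreviation list is not an operational definition.** It also ties PFS to the olaparib period, which 8.3.2 does not. That is fair, but the point does not rest on the list alone. The stated outcome measure is time to a second progression, and in case 1 the rule returns a third progression or death.

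**The SAP may settle it.** Section 8.4.2 leaves further detail on secondary variables to the SAP, which is not at hand. For case 2 that may be enough. For case 1 the protocol already states a rule, and the rule gives the wrong event.

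**The consequence is small.** PFS2 is descriptive, and every shift in the table is below one assessment interval (12 × 7 / 30.4 = 2.8 months). This stands and limits the weight of the point.

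A reader might go further in three ways, none of which the documents support:

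- That every change of therapy before RECIST progression is miscounted. A patient who switches for toxicity or by choice, with no progression, has her genuine first progression at the later RECIST event.
- That PFS2 is undefined, or lengthened, in case 2. The gloss and section 4.3.3 offer a workable reading, death still counts, and no direction of error follows from the text.
- That each case 1 patient is late by a whole further line of therapy. Death before the third progression ends PFS2 sooner.

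**Conclusion.** The point holds in two parts. In case 1 the stated rule takes a second progression as the first and so lengthens PFS2; the direction follows from the text. In case 2 the protocol supports two readings and should choose one.

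The size is not known from the documents, which give neither the affected share nor the third gap. The rise of about 0.3 to 2.4 months in median PFS2 rests on assumed values for both, on exponential times, on TSST as a stand-in for PFS2, and on ignoring death before the later progression. It is an illustration, not an estimate.

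The effect is confined to a descriptive secondary endpoint. The PFS definition, the co-primary analyses and the 150-event trigger do not depend on it. It is worth correcting because the change is small and the present wording gives an event that is not the second progression.

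**What to change.** In sections 8.3.3 and 4.3.3 and the second-progression row of Table 3, define the first progression for PFS2 as the earliest investigator-recorded progression by any criterion (RECIST, symptomatic or CA-125), whether or not it counts as a PFS event. Then state that:

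- a RECIST progression on a subsequent therapy started after such a non-RECIST progression is the PFS2 event, and remains the PFS event;
- a progression censored for PFS because of missed visits still serves as the first progression for PFS2;
- for patients who changed therapy without any progression, which reading applies: second progression, or progression on the subsequent therapy as the abbreviation list suggests.

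Do not use the start of subsequent therapy alone as the anchor. For a patient who switched without progressing, it would label her first progression as the second and make PFS2 equal to PFS.

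The cost is derivation wording and an aligned Table 3 row. Later therapies, responses to them and progression dates after olaparib are already recorded (footnotes to Tables 2 and 3). One item needs checking: the footnotes do not expressly require the date of a symptomatic or CA-125 progression that led to stopping, so confirm that the eCRF holds it.

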8.4.1 Analysis of the primary variable

PFS will be analysed when approximately 150 progression events among patients with *BRCA* mutated ovarian cancer have occurred in the study (60% maturity). At this point, it is expected that 30 progression events (60% maturity) would have occurred in the cohort of at least 50 patients with *sBRCA*m disease. PFS analyses will be performed in the cohort of patients with *sBRCA*m disease and all *BRCA*m patients, both assessed according to RECIST 1.1 guidelines, to address the co-primary objectives of the study.

Kaplan-Meier (KM) plots of PFS will be presented for the cohort of patients with *sBRCA*m disease and for all patients with *BRCA*m disease. Summaries of the number and percentage of patients experiencing a PFS event, and the type of event (progression or death) will be provided along with median PFS and 95% confidence intervals.

The analyses on PFS will be based on investigator assessments according to RECIST 1.1 guidelines, and using all scans regardless of whether they were scheduled or not. The estimated PFS rates at 6 months, 12 months and 24 months will be summarised (using the KM curves) for the cohort of patients with *sBRCA*m disease and for all patients with *BRCA*m disease.

The number of patients prematurely censored will be summarised together with baseline prognostic factors of the prematurely censored patients. A patient is defined as prematurely censored if they had not progressed and the latest scan prior to DCO was more than 1 scheduled tumour assessment interval (+ 2 weeks) prior to the DCO date.

The analyses of PFS will be repeated on the exploratory HRRm cohort.

8.4.2 Analysis of the secondary variable(s)

All time to event endpoints (OS, PFS2, TFST, TSST, and TDT) will be described as for PFS in the subset of patients with *sBRCA*m disease, and for all patients with *BRCA*m disease. A summary of PFS2 and OS will be produced at the time of the PFS data cut off. Descriptive analyses will be performed on all QoL endpoints, using frequency distribution for categorical endpoints and means and corresponding 95% confidence intervals for continuous endpoints. The analyses of OS will be repeated on the exploratory HRRm cohort. Further details will be provided in the Statistical Analysis Plan.

Safety data will be summarised and reported for all patients with *BRCA*m, patients with *sBRCA*m and patients with HRRm ovarian cancer.

8.4.3 **Subgroup analysis**

Among patients with *BRCA*m disease, subgroup analyses will be presented, as described for the primary analysis of PFS, to assess the consistency of olaparib effect across potential or expected prognostic factors.

The following subgroups of the FAS may be summarised.

- Response to previous platinum chemotherapy (CR vs PR)
- Time to disease progression on last platinum based chemotherapy received prior to first dose of olaparib (6 12 months / > 12 months)
- Measurable versus non-measurable disease at baseline
- *BRCA* mutation type, e.g. *gBRCA*; *BRCA1*, *BRCA2* or *BRCA1/2* (both)
- Age at enrolment (<65 vs \geq 65 years old)
- Region
- Prior PARP inhibitor use
- Family history
- Prior bevacizumab use.

Other baseline variables may also be assessed if there is clinical justification. Further explorations will be undertaken for patient characteristics within germline and somatic *BRCA* mutated disease groups. Details will be provided in the Statistical Analysis Plan.

8.4.4 Interim analysis

No formal statistical interim analyses for PFS are planned for this trial.

8.4.5 **Exploratory analysis (if applicable)**

Exploratory translational science endpoints

Full statistical methods for biomarker exploratory endpoints will be defined in a separate translation science analysis plan. Biomarker data will be summarised descriptively using tables and plots. If the data is available at the time of developing the CSR then the biomarker data will be included in the CSR. Otherwise the biomarker data will be reported in a separate addendum to the CSR (if applicable). Further details on the data summaries and plots for the biomarker data for the CSR will be provided in the SAP.

8.5 **Training of study site personnel**

Before the first patient is entered into the study, a designated AstraZeneca representative will review and discuss the requirements of the Clinical Study Protocol and related documents with the investigational staff and also train them in any study specific procedures and the WBDC and/or any electronic PROs system(s) utilised.

The PI will ensure that appropriate training relevant to the study is given to all of these staff, and that any new information relevant to the performance of this study is forwarded to the staff involved.

The PI will maintain a record of all individuals involved in the study (medical, nursing and other staff).

8.6 Monitoring of the study

During the study, an AstraZeneca representative will have regular contacts with the study site, including visits to:

- Provide information and support to the Investigator(s)
- Confirm that facilities remain acceptable
- Confirm that the investigational team is adhering to the protocol, that data are being accurately and timely recorded in the CRFs, that biological samples are handled in accordance with the Laboratory Manual and that study drug accountability checks are being performed
- Perform source data verification (a comparison of the data in the CRFs with the patient's medical records at the hospital or practice, and other records relevant to the study) including verification of informed consent of participating patients. This will require direct access to all original records for each patient (e.g., clinic charts)
- Ensure withdrawal of informed consent to the use of the patient's biological samples is reported and biological samples are identified and disposed of/destroyed accordingly, and the action is documented, and reported to the patient.

The AstraZeneca representative will be available between visits if the Investigator(s) or other staff at the centre needs information and advice about the study conduct.

